Specific Aim 3: Describe differences in outcomes between participants with and without previous history of COVID-19 diagnosis

Primary Outcomes:

- VO₂ max during CPET
- Test duration (time) on a CPET
- Reaction time (measured in milliseconds) and percentage accuracy on the SRT task

Secondary Outcomes:

- Minute ventilation (VE) at max during CPET
- Subjective dyspnea rating (Borg) during CPET
- Subjective exertion rating (Borg) during CPET
- O₂ saturation at baseline, each stage, and recovery during CPET
- Blood pressure at baseline, each stage, and recovery during CPET
- Max heart rate during CPET
- Respiratory quotient at max during CPET
- Blood lactate during CPET

[figure not shown]
INVESTIGATIONAL PLAN

Research Design and Methodology

Phase I:

In this prospective, randomized crossover trial of eligible athletes, we will compare VO₂ max during two maximal cardiopulmonary stress exercise tests (CPET), seven to ten days apart. Subjects will be randomized into either the face covering or non-face covering group using a 1:1 randomization scheme, stratified by sex, and will serve as their own control in the subsequent test seven to ten days later (see Figure 1. Randomization diagram, below). A within-subjects analysis will be performed stratified by sex.

[figure not shown]
Figure 1. Phase I Randomization diagram

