**Phase II:**

In this prospective, randomized crossover trial of 50 eligible participants, we will compare two maximal cardiopulmonary stress exercise tests (CPET) on a cycle ergometer, seven to ten days apart, and the impact on cognitive performance. ECG monitoring will take place during exercise testing among individuals with history of COVID-19. Subjects will be randomized into either the face covering or non-face covering group using a 1:1 randomization scheme, stratified by prior COVID-19 diagnosis, and will serve as their own control in the subsequent test (see Figure 2. Randomization diagram, below). A within-subjects analysis will be performed stratified by sex.

Cognitive testing will take place at the end of each stage of the CPET. Cognitive testing using the SACL Cognition application on iPad will include a baseline SRT measurement and additional measurements at the end of each stage of the CPET. The baseline will include a 30s session of SRT for familiarization and then a 30s session will be scored. SRT will then be administered for 30s at the end of each stage of the CPET. The SRT task includes a visual stimulus presented on the touchscreen. Subjects will be instructed to press the stimulus on-screen as quickly as possible. Reaction time and accuracy will be measured on the SRT task. Reaction time is calculated as the average amount of time in seconds between stimulus presentation and user response within a session. Accuracy is calculated as the total number of correct responses to stimuli divided by the total number of stimuli presented during a session (presented as a percentage).

Figure 2. Phase II Randomization diagram

Phase I: Eligibility Criteria

Inclusion Criteria	Rationale
18-29 years of age	Younger and older individuals are excluded to reduce variability of lung volume outcomes. Herdy, A. H. & Uhlendorf, D. (2010) Reference values for cardiopulmonary exercise testing for sedentary and active men and women. Sociedade Brasileira de Cardiologia.

Exclusion Criteria	Rationale
Orthopedic or neurologic, or other limitations	Individuals with limitations that would not allow for exercise testing on a treadmill are excluded.
Previous or current diagnoses for cardiopulmonary conditions	Individuals with conditions for which a healthcare provider has discouraged high-intensity exercise are excluded (e.g., arrhythmia, pacemakers, Wolfe Parkinson White syndrome).

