Presence of beards	Beards interfere with the fit of the Vo2 mask. Therefore, participants with beards will be asked to shave prior to their visit. If they are unwilling to shave, they will not be eligible for the study.
Claustrophobia	Participants who have been diagnosed or treated for claustrophobia will be excluded. Claustrophobia is a contraindication of the CPET test.
Currently experiencing symptoms of COVID-19 or < 7 days since last symptoms	Participants will be screened for COVID-19 symptoms using the BSW COVID-19 screener; if participants have past history of COVID-19 based on laboratory testing, participants will be ineligible if <7 number of days since last symptoms

Study Procedures

Phase I & II Subject Recruitment

Up to 100 participants (50 for each phase) will be recruited from Baylor Scott & White Sports Therapy and Research at The Star in Frisco, Texas through approved fliers, calls, emails, and social media, as well as through local community organizations, healthcare clinics, and collaborating centers and organizations, including but not limited to the Sports Academy and the University of North Texas. IRB-approved fliers will be posted at BSW The Star and at affiliated organizations and collaborators in the DFW Metroplex and surrounding areas. In addition, members of the study team will attend meetings with local clinicians and community partners to inform them of the purpose of the study. The study flier will contain information on the study and methods to contact the study team including (1) a QR code linked to the eligibility screener which will be stored in a REDcap, a HIPAA-compliant (21 CFR Part 11) secure web application, (2) a phone number, and (3) an email address of the study coordinator. Interested individuals may contact the study team by phone or email to learn more about the study and undergo a telephone screener or follow the QR code to complete the eligibility screener electronically. A snowball sampling technique will be used for further recruitment whereby interested participants will be invited to ask other athletes they know to contact the study team about participation. Eligible individuals will be contacted by a member of the study team to schedule their first study visit. It is anticipated that recruitment will take 2-4 weeks during each phase to achieve our desired sample size.

Subject Information and Screening

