Participant characteristics will be summarized with means and standard deviations or medians and interquartile ranges for numerical variables, and counts and percentages for categorical variables. The primary outcomes, VO₂ max and test duration, will first be assessed for normality using a Kolmogorov-Smirnov test prior to determining the analysis to be used. If the distribution meets the normality assumption, paired t-tests will be used to determine if there is a difference between participants when wearing and not wearing a face covering. If the distribution does not meet the normality assumption, Wilcoxon signed-rank tests will be used. All secondary outcomes will follow the same analysis plan of assessing the normal distribution assumption to determine the appropriate test for each outcome. Inter-rater reliability analysis will be conducted for the Attitudes for Face Coverings Questionnaire. All analysis will be performed using SAS 9.4 at a 0.05 significance level.

Risks & Benefits

- Physical risks: The potential risks include any and all risks associated with exercise including muscular injury, increased blood pressure and heart rate, and cardiac arrest. Other risks include hypoglycemia post-exercise and lightheadedness or syncope. Although some risks are unavoidable, the careful monitoring of signs and symptoms by the subject and clinical staff will minimize these risks.
- No psychological risks have been identified by participating in this study.
- No social risks have been identified by participating in this study.
- No economic risks have been identified by participating in this study.
- No legal risks have been identified by participating in this study.
- Potential benefits: Participants in this study may experience greater confidence in performing aerobic activities and may gain a better understanding of their personal functional exercise capacity at the time of testing. Participants may also better understand their body's response to exercise with and without a face covering which may impact training and performance in recreational and occupational ventures.

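### The design section calls for an analysis stratified by sex, but Data Analysis names only a pooled paired test with no sex or period term, and the plan does not say what the stratification means

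*Combined protocol and SAP*

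**What the plan says.** Under Research Design and Methodology, the Phase I paragraph randomises test order 1:1 within sex and ends: "A within-subjects analysis will be performed stratified by sex". The Phase II paragraph ends with the same sentence, although its own randomisation is "stratified by prior COVID-19 diagnosis, and will serve as their own control in the subsequent test". The Randomization section, which covers both phases, gives sex as the only stratification factor.

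Data Analysis is the only section that names a test. It starts with a normality check: VO₂ max and "test duration, will first be assessed for normality using a Kolmogorov-Smirnov test prior to determining the analysis to be used". If normality is accepted, "paired t-tests will be used to determine if there is a difference between participants when wearing and not wearing a face covering". Otherwise: "If the distribution does not meet the normality assumption, Wilcoxon signed-rank tests will be used". Secondary outcomes follow the same route. The section contains no sex term, period term, by-sex reporting, interaction test or multiplicity rule. It sets one error level: "All analysis will be performed using SAS 9.4 at a 0.05 significance level".

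On numbers, the recruitment section says: "Up to 100 participants (50 for each phase) will be recruited". No effect size, SD of the within-person differences, target power or planned split of men and women appears anywhere.

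**The concern.** The two sections describe the analysis of the same data differently, and the word stratified does not settle the difference. It can mean a separate paired test in each sex, one test that combines the two sexes, or a pooled test with results also shown by sex. These do not answer the same question. The first gives two p-values per outcome, each from part of the sample, with no rule for what counts as a positive result. The second and third give one.

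Without a statement of which result answers Phase I Aim 2, that choice could be made after the data are seen. Phase II has a further gap: the factor used to randomise is given two ways, and one of them does not match the factor named for the analysis.

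**Working it through.** **Inputs from the documents.** Up to 50 participants per phase; significance level 0.05. Sidedness is not stated; two-sided is taken from the wording "to determine if there is a difference between participants". The plan gives no power figure to reproduce.

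**Assumptions.** Standardised paired effect d (mean within-person difference divided by its SD) of 0.3 to 0.8; all 50 complete both tests; 25 men and 25 women, with 30/20 and 35/15 as alternatives.

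**Formula.** Power is the probability that a noncentral t variable with n − 1 degrees of freedom and noncentrality d√n exceeds the two-sided 5% critical value in absolute size. The combined stratified test uses all 50 people and loses one degree of freedom (48).

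At d = 0.4:
- Pooled, n = 50: noncentrality 0.4 × √50 = 2.83, critical value 2.01, power 79.2%.
- Combined stratified, n = 50, 48 degrees of freedom: power 79.1%.
- One sex alone, n = 25: noncentrality 0.4 × √25 = 2.00, critical value 2.06, power 48.4%.

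| Assumed d | Pooled, n = 50 | Combined stratified, n = 50 | One sex, n = 25 |
|---|---|---|---|
| 0.3 | 54.8% | 54.7% | 30.2% |
| 0.4 | 79.2% | 79.1% | 48.4% |
| 0.5 | 93.4% | 93.4% | 67.0% |
| 0.6 | 98.6% | 98.6% | 82.1% |
| 0.8 | about 100% | about 100% | 97.0% |

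Uneven splits at d = 0.4: 30/20 gives 56.3% and 39.7%; 35/15 gives 63.3% and 30.3%.

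**Decision rules for two separate tests at d = 0.4.** Power and error must come from the same rule.
- Either sex significant: power 1 − (1 − 0.484)² = 73%; false-positive chance with no effect in either sex 1 − 0.95² = 9.75%.
- Both sexes significant: power 0.484² = 23%; false-positive chance 0.05² = 0.25%.

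The documents state neither rule.

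**Period.** Suppose results shift between the first and second test by 0.5 SD of the differences, with 25 people in each order. The plain paired test counts that shift as noise: its SD is inflated by about √(1 + 0.5²) = 1.12. By simulation, its power at d = 0.4 falls from 79% to 72%, while a period-adjusted test stays at 79%.

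**The case against.** A reader might infer that the plan contains two rival primary analyses with very different power. The documents do not support that. The design sentence names no test and does not call its analysis primary; only Data Analysis says how the primary outcomes are tested. A natural reading is that the paired test is primary and results are also shown by sex, and both can be done. Nor can it be said that the stratum is ignored under every reading: the sentence speaks of one analysis, which could be a single combined stratified test.

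The power loss arises under one reading only, and its size depends on inputs that the plan does not give. Among the effects tabulated, 0.4 SD shows nearly the widest gap, about 31 percentage points; at 0.8 SD it is about 3. Nor may the 23% power be set beside the 9.75% error, because they belong to different rules.

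It is also fair to say that each person is their own control, so a person's sex cancels from the within-person difference unless the mask effect itself differs by sex. Adjusting for sex therefore gains little.

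All of this stands, and it limits the point to an unresolved definition. It does not answer which result addresses Aim 2, or explain the Phase II mismatch.

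**Conclusion.** The mismatch is real in both phases and should be resolved before analysis. The plan promises a sex-stratified analysis, specifies a test that does not mention sex, and defines neither the meaning nor the status of the stratification.

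If a combined test or supportive summaries were meant, power is unaffected. If separate tests at 0.05 were meant, power in each sex would be 30%, 48%, 67% and 97% at 0.3, 0.4, 0.5 and 0.8 SD, against 55%, 79%, 93% and about 100% pooled, and an either-sex claim would carry a 9.75% false-positive chance per outcome. These figures rest on an assumed 25 per sex, no dropout and two-sided testing; since 50 is a ceiling, actual power could be lower throughout. The strongest reason to act is that one named analysis removes a choice that could otherwise follow the results, at essentially no cost in power.

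**What to change.** In Data Analysis:

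1. Name one primary within-person analysis per primary outcome, in all participants of the phase. A suitable form is a linear model for the difference (covered minus uncovered) with test order coded ±1, which adjusts for period, and the randomisation stratum. In Phase I that stratum is sex, centred at its sample mean so that the intercept is the overall average mask effect. With three parameters and 50 people (47 degrees of freedom), power at 0.4 SD is still 79%.
2. State that by-sex mask effects are supportive, reported with 95% confidence intervals and a mask-by-sex interaction, not as separate significance tests. In the model above, the sex coefficient is that interaction.
3. Say what becomes of the signed-rank branch. It could be kept as a sensitivity analysis, so that one named method carries the primary result.
4. For Phase II, reconcile the design paragraph (randomisation by prior COVID-19 diagnosis, analysis by sex) with the Randomization section (by sex), and adjust for the stratum actually used.
5. Amend the design sentence in both phases to refer to Data Analysis.

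The cost is wording and two model terms. Sex is already collected and test order is known from the randomisation; no extra participants, visits or measurements are needed.

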**Phase II:**

In this prospective, randomized crossover trial of 50 eligible participants, we will compare two maximal cardiopulmonary stress exercise tests (CPET) on a cycle ergometer, seven to ten days apart, and the impact on cognitive performance. ECG monitoring will take place during exercise testing among individuals with history of COVID-19. Subjects will be randomized into either the face covering or non-face covering group using a 1:1 randomization scheme, stratified by prior COVID-19 diagnosis, and will serve as their own control in the subsequent test (see Figure 2. Randomization diagram, below). A within-subjects analysis will be performed stratified by sex.

Cognitive testing will take place at the end of each stage of the CPET. Cognitive testing using the SACL Cognition application on iPad will include a baseline SRT measurement and additional measurements at the end of each stage of the CPET. The baseline will include a 30s session of SRT for familiarization and then a 30s session will be scored. SRT will then be administered for 30s at the end of each stage of the CPET. The SRT task includes a visual stimulus presented on the touchscreen. Subjects will be instructed to press the stimulus on-screen as quickly as possible. Reaction time and accuracy will be measured on the SRT task. Reaction time is calculated as the average amount of time in seconds between stimulus presentation and user response within a session. Accuracy is calculated as the total number of correct responses to stimuli divided by the total number of stimuli presented during a session (presented as a percentage).

Figure 2. Phase II Randomization diagram

Phase I: Eligibility Criteria

Inclusion Criteria	Rationale
18-29 years of age	Younger and older individuals are excluded to reduce variability of lung volume outcomes. Herdy, A. H. & Uhlendorf, D. (2010) Reference values for cardiopulmonary exercise testing for sedentary and active men and women. Sociedade Brasileira de Cardiologia.

Exclusion Criteria	Rationale
Orthopedic or neurologic, or other limitations	Individuals with limitations that would not allow for exercise testing on a treadmill are excluded.
Previous or current diagnoses for cardiopulmonary conditions	Individuals with conditions for which a healthcare provider has discouraged high-intensity exercise are excluded (e.g., arrhythmia, pacemakers, Wolfe Parkinson White syndrome).
Medical diagnosis of diabetes and/or currently on medications for diabetes (e.g., insulin)	Individuals with a diagnosis of diabetes and/or individuals currently taking medications for diabetes will be excluded, as the results from their VO2max tests would not be comparable to the testing sample.
Uncontrolled asthma	Individuals with conditions for which a healthcare provider has discouraged high-intensity exercise are excluded.
Inmates	Protected population.
Pregnancy	Protected population.
History of previous positive COVID-19 test	Individuals who have previously tested positive for COVID-19 will be excluded from the current study due to possible cardiopulmonary implications.
Presence of beards	Beards interfere with the fit of the Vo2 mask. Therefore, participants with beards will be asked to shave prior to their visit. If they are unwilling to shave, they will not be eligible for the study.
Claustrophobia	Participants who have been diagnosed or treated for claustrophobia will be excluded. Claustrophobia is a contraindication of the CPET test.

Phase II: Eligibility Criteria

Inclusion Criteria	Rationale
18-39 years of age	Younger and older individuals are excluded to reduce variability of lung volume outcomes. Herdy, A. H. & Uhlendorf, D. (2010) Reference values for cardiopulmonary exercise testing for sedentary and active men and women. Sociedade Brasileira de Cardiologia.

Exclusion Criteria	Rationale
Orthopedic or neurologic, or other limitations	Individuals with limitations that would not allow for exercise testing on a treadmill are excluded.
Previous or current diagnoses for cardiopulmonary conditions	Individuals with conditions for which a healthcare provider has discouraged high-intensity exercise are excluded (e.g., arrhythmia, pacemakers, Wolfe Parkinson White syndrome).

Medical diagnosis of diabetes and/or currently on medications for diabetes (e.g., insulin)	Individuals with a diagnosis of diabetes and/or individuals currently taking medications for diabetes will be excluded, as the results from their VO2max tests would not be comparable to the testing sample.
Uncontrolled asthma	Individuals with conditions for which a healthcare provider has discouraged high-intensity exercise are excluded.
Inmates	Protected population.
Pregnancy	Protected population.
Presence of beards	Beards interfere with the fit of the Vo2 mask. Therefore, participants with beards will be asked to shave prior to their visit. If they are unwilling to shave, they will not be eligible for the study.
Claustrophobia	Participants who have been diagnosed or treated for claustrophobia will be excluded. Claustrophobia is a contraindication of the CPET test.
Currently experiencing symptoms of COVID-19 or < 7 days since last symptoms	Participants will be screened for COVID-19 symptoms using the BSW COVID-19 screener; if participants have past history of COVID-19 based on laboratory testing, participants will be ineligible if <7 number of days since last symptoms

Study Procedures

Phase I & II Subject Recruitment

Up to 100 participants (50 for each phase) will be recruited from Baylor Scott & White Sports Therapy and Research at The Star in Frisco, Texas through approved fliers, calls, emails, and social media, as well as through local community organizations, healthcare clinics, and collaborating centers and organizations, including but not limited to the Sports Academy and the University of North Texas. IRB-approved fliers will be posted at BSW The Star and at affiliated organizations and collaborators in the DFW Metroplex and surrounding areas. In addition, members of the study team will attend meetings with local clinicians and community partners to inform them of the purpose of the study. The study flier will contain information on the study and methods to contact the study team including (1) a QR code linked to the eligibility screener which will be stored in a REDcap, a HIPAA-compliant (21 CFR Part 11) secure web application, (2) a phone number, and (3) an email address of the study coordinator. Interested individuals may contact the study team by phone or email to learn more about the study and undergo a telephone screener or follow the QR code to complete the eligibility screener electronically. A snowball sampling technique will be used for further recruitment whereby interested participants will be invited to ask other athletes they know to contact the study team about participation. Eligible individuals will be contacted by a member of the study team to schedule their first study visit. It is anticipated that recruitment will take 2-4 weeks during each phase to achieve our desired sample size.

Subject Information and Screening

Eligible individuals will be screened by trained study coordinators via telephone using the Eligibility Script. If a participant is ineligible based on the screening tool, they will be thanked for their time and informed that they are not able to participate further. If a participant is eligible based on the screening tool, they will be asked to schedule a baseline assessment appointment where informed consent will be obtained. All individuals will be given a screening ID number and all screening information will be input into a password-protected subject tracking database.

COVID-19 Screening

Participants will be instructed to wear face coverings from the parking lot and inside the building. Prior to participation in the CPET, subjects will complete the BSWH COVID-19 screening (procedure outlined in supplementary materials) and a temperature check with a TIR-1 thermometer (procedure outlined in supplementary materials) outside of testing environment. If the subject screens positive or has a temperature of over 100 degrees, subject will not be able to participate in the study and instructed to leave the facility and

comply with current state and local recommendations. If the subject screens negative on both assessments, subject will be taken into testing area for CPET testing.

Informed Consent

Informed consent will be obtained by study staff in person at the beginning of their study visit and prior to any study related procedures taking place. Informed consent will be conducted in a private location using similar procedures as described above by trained study staff to minimize coercion. Participants will be informed about the study, have sufficient time to review the consent form, and all study questions will be answered prior to signature. Participants will be given sufficient opportunity to decide whether or not they want to participate. If the participant elects to enroll in the study, they will be instructed on how to sign the consent form and a copy will be given to them prior to the initiation of any study procedures.

Randomization

Phase I & II: Participants meeting the inclusion and exclusion criteria will be approached, screened, consented, and enrolled into the study. After obtaining informed consent, participants will be randomized to either complete their first test with no face covering or with a face covering in a 1:1 randomization ratio stratified by sex. A random number generator will be used to pre-determine the randomization group for each participant ID number. The group assignment will be not be revealed to either the participant or the study staff until informed consent is complete.

Cardiopulmonary Exercise Testing (CPET)

During the screening process, subjects will be encouraged to abstain from nicotine and caffeine prior to the test. Subjects will be scheduled to perform a CPET on a treadmill with (arm 1) and without (arm 2) a face covering (with testing for each arm seven to ten days apart). A face covering will be provided to participants randomized into the face covering group, with the option for participants to keep their face covering at the end of the assessment. Subjects will be fitted for metabolic testing (K5 CPET, COSMED, Concord, CA) equipment according to factory requirements. <https://www.cosmed.com/en/products/cardio-pulmonary-exercise-test/k5>

The use of new cloth face coverings beneath the K5 mask will be standardized, with face coverings consisting of the same material and cut/design for each participant (which the participant then keeps or discards). The correct fitting and leak tightness will be confirmed before each test for each subject. This will be achieved through (a) inspiration and (b) expiration with maximal force. During both maneuvers, the valve of the mask is closed leading to abrupt stop of the air flow. The fitting is carefully checked for the absence of any acoustic, sensory or visual indication of leakage (e.g., lifting of the mask, whistling or lateral airflow) by the investigators and the test person.

Phase I CPET Procedures:

The CPET will be performed in an area with immediate access to an automated external defibrillator (AED). Resting blood pressure, heart rate, pulse oxygenation and will be measured and recorded. Explanation of the Borg dyspnea and exertion scales will occur by an Exercise Physiologist prior to beginning test. Each subject will be asked to perform the exercise test to the best of their abilities. At the beginning of the test, subjects will be instructed to perform a walking warm up of 3 minutes at 1.7 speed and 0% incline.

- The Borg Rating of Perceived Exertion (6-20) scale will be used during the test to assess subjective exertion
- The Modified Borg Dyspnea Scale (0-10) will be used to assess subjective shortness of breath.
- Intermittent blood pressure measurements and pulse oximeter measurements will be taken by an exercise physiologist and heart rate will be monitored constantly.

Testing will be terminated if any of the following occurs: (a) subject becomes symptomatic; (b) pain is reported; (c) subject wishes to terminate test; (d) unsafe drop in blood pressure or hypertension over 250/120 mmHg reported; or (e) subject reports a “20” on Borg RPE scale or “10” on Dyspnea scale. Other termination of the test is reserved for the clinical judgment of research staff to ensure safety of the subject. After termination

of the test, subject will be instructed to perform a walking cool-down of 3 to 5 minutes. After subject has completed cool-down, recovery blood pressure, heart rate and pulse oxygenation will be measured and recorded. After completion of the first test, subject will be scheduled for second CPET 7-10 days later to allow for adequate recovery. When data collection is complete, CPET data will be gathered from metabolic cart and matched with subject testing materials.

Phase II CPET Procedures:

Among individuals with history of COVID-19, an ECG will be performed prior to CPET procedures and will be monitored throughout the CPET.

The CPET will be performed in an area with immediate access to an automated external defibrillator (AED). Resting ECG (among individuals with history of COVID-19), blood pressure, heart rate, pulse oxygenation, and blood lactate will be measured and recorded. Explanation of the Borg dyspnea and exertion scales will occur by an Exercise Physiologist prior to beginning test. Each subject will be asked to perform the exercise test to the best of their abilities.

A standard cycle ergometry ramp protocol⁷ will be designed for each participant as used in previous masking study.⁸ The initial workloads and incremental increases will be determined based on the subject's age and weight. The protocol consists of 1 minute of unloaded cycling, followed by a 2-minute warmup at 25 W. The exercise phase consists of continuous progressive increases in power output (25 W · min⁻¹) every three minutes until the subject is unable to maintain 50 rpm. This is followed by 4 min of active recovery at 20 W.

- The Borg Rating of Perceived Exertion (6-20) scale will be used during the test to assess subjective exertion
- The Modified Borg Dyspnea Scale (0-10) will be used to assess subjective shortness of breath.
- Intermittent blood pressure measurements and pulse oximeter measurements will be taken by an exercise physiologist and heart rate will be monitored constantly.
- Blood lactate will be measured pre and post-CPET using a Nova Medical Lactate Plus: Blood Lactate Measuring Meter-Version 2 device.

Testing will be terminated if any of the following occurs: (a) subject becomes symptomatic; (b) pain is reported; (c) subject wishes to terminate test; (d) unsafe drop in blood pressure or hypertension over 250/120 mmHg reported; or (e) subject reports a “20” on Borg RPE scale or “10” on Dyspnea scale. Other termination of the test is reserved for the clinical judgment of research staff to ensure safety of the subject. After termination of the test, subject will be instructed to perform a cycling cool-down of 3 to 5 minutes. After subject has completed cool-down, recovery blood pressure, heart rate and pulse oxygenation will be measured and recorded. After completion of the first test, subject will be scheduled for second CPET 7-10 days later to allow for adequate recovery. When data collection is complete, CPET data will be gathered from metabolic cart and matched with subject testing materials.

Disinfection Procedures

All equipment will be disinfected between each subject contact using BSWH approved disinfectant wipes (sani cloths AF3) using Cidezyme and Cidex OPA with testing strips as per factory requirements. This process will take place in a designated “dirty room” to perform high level disinfecting (e.g., sink and proper ventilation) and has been approved by BSWH Infection Prevention and is effective against COVID-19 spread in addition to other high-consequence infectious diseases (procedure provided in supplementary procedures).

Data Collection Details

All data will be collected during each study visit on paper case report forms or via direct data entry in the study's REDCap database. Complete paper case report forms will be entered in the REDCap database within 3 days of collection. Sources for data include patient reported data and objective results from CPET evaluation.

Staff Training

All study staff will be trained on study procedures at the project launch meeting and subsequent support meetings.

Venue

In-person sessions will take place at BSW Sports Therapy and Research at The Star in Frisco, Texas.

Communication

To facilitate appointment scheduling and timely ongoing communication between study staff and participants, study staff will communicate with participants via their preferred methods of communication (established during screening), whether phone, email, or text message. All communication will be documented on communication logs that will be kept in patient files or in electronic communication logs stored in Excel. Participants will be asked not to transmit sensitive health information via text message, but will be given a secure email message that they can reply to when communicating sensitive health information digitally. Participants will be informed that they may be responsible for charges incurred by text messages.

Study Testing Visits

Participants will be asked to come in at two time points for measurements, surveys, and testing.

Schedule of Assessments**Phase I:**

Study Visit	Visit Details
Initial visit/Visit 1	
 • COVID-19 screening and temperature check is performed • Demographic information (age, race, ethnicity, sex, income, insurance, work history, sport) • Clinical and physical activity information (Physical activity readiness questionnaire, physical activity history, tobacco use, marijuana use, vaping, history of asthma, height, weight, use of beta-blockers) • Attitudes Towards Face Coverings Questionnaire • Cardiopulmonary exercise testing (CPET) 
 ◦ Dyspnea scores ◦ Exertion scores ◦ Pulse ox measurements ◦ Blood pressure measurements • Scale of Measuring Subjective Perceptions • Participant will be scheduled for 2nd CPET
Visit 2	
 • COVID-19 screening and temperature check is performed • Attitudes Towards Face Coverings Questionnaire • Cardiopulmonary exercise testing (CPET) 
 ◦ Dyspnea scores ◦ Exertion scores ◦ Pulse ox measurements ◦ Blood pressure measurements • If subject is randomized to face covering: Qualitative question describing experience • Quantitative and qualitative questions about difficulty of wearing face coverings during CPET and differences completing the CPET with and without a face covering. • Scale of Measuring Subjective Perceptions

Phase II:

Study Visit	Visit Details
Initial visit/Visit 1	
 COVID-19 screening and temperature check is performed Demographic information (age, race, ethnicity, sex, income, insurance, work history, sport) If subject reports a previous COVID-19 diagnosis: information regarding symptoms, severity, hospitalization, health changes, experience while exercising, and vaccinations will be collected. Clinical and physical activity information (Physical activity readiness questionnaire, physical activity history, tobacco use, marijuana use, vaping, history of asthma, height, weight, use of beta-blockers) Attitudes Towards Face Coverings Questionnaire ECG among individuals with history of COVID-19 Cardiopulmonary exercise testing (CPET) 
 Heart rate Dyspnea scores Exertion scores Pulse oximetry measurements Blood pressure measurements Lactate measurements (pre and post-CPET) Scale of Measuring Subjective Perceptions Participant will be scheduled for 2nd CPET
Visit 2	
 COVID-19 screening and temperature check is performed Attitudes Towards Face Coverings Questionnaire ECG among individuals with history of COVID-19 Cardiopulmonary exercise testing (CPET) 
 Heart rate Dyspnea scores Exertion scores Pulse oximetry measurements Blood pressure measurements Lactate measurements (pre and post-CPET) When subject is randomized to face covering: Qualitative question describing experience Quantitative and qualitative questions about difficulty of wearing face coverings during CPET and differences completing the CPET with and without a face covering. Scale of Measuring Subjective Perceptions

Compensation and Costs

While we will not pay participants for taking part, participants will be reimbursed a \$50 Visa gift card for their time/effort to attend each of the assessments (two) which are required for research for a total of \$100. Participants will be given the option to keep their face covering that was given to them during CPET testing. Participants will not incur any additional research-related costs due to study participation.

Data Protection & Confidentiality

In order to assure participant confidentiality, all participants will be assigned a unique study identification number. Only one master list will be maintained by the PI and the study coordinator on a secure network drive in a password protected file. All case report forms and databases will use the subject ID number rather than names or other private health information and entered into REDCap. All paper documentation, including

signed paper consent forms and case report forms will be maintained by the PI behind a locked door in a locked file cabinet.

All participants that are screened will be given a screening identification number. Screening reports will not use private health information and will only refer to patients using the screening identification number. After consent, participants will be given a unique subject ID. All documents thereafter will refer to the participant by subject ID. All screening and enrollment data will be tracked on a password protected enrollment tracking spreadsheet which will also contain the link to identifiers. Only authorized study personnel will have access to this database. All data will be shared on the secured Baylor Network Onedrive server.

